## 5.9 Assessing Expectedness

Expected adverse events are adverse events consistent with the applicable product information provided by the sponsor (the investigator’s brochure for an investigational product). The sponsor, in the person of the local medical monitor, determines expectedness. If the assessment is that the adverse event is **expected** no further action is required. If the local medical monitor’s assessment is that the adverse event is **unexpected**, then the event may represent a SUSAR or expedited SAE (see Sections 5.10 and 5.11).

## 5.10 Definition of Suspected Unexpected Serious Adverse Reaction (SUSAR)

When an adverse event is judged to be related to an investigational product, such as SYN023 and also is judged to be serious and unexpected, it is a SUSAR (suspected unexpected serious adverse reaction) and is subject to expedited reporting.

### **5.11 Reporting of Serious Adverse Events**

***Serious adverse events, which include SUSARs, are reported to the sponsor and to Drug Safety Solutions for the entire study period (see protocol appendices). SUSARs are reported even after the trial is over, if the sponsor, local medical monitor or principal investigator becomes aware of them.*** The site will be provided with specific reporting procedures including the Adverse Event CRF and any supplemental reporting forms to be used. Serious adverse events will be reported on the Adverse Event CRF using a recognized medical term or diagnosis that accurately reflects the event.

Serious adverse events will be assessed by the investigator and the local medical monitor according to their roles (as described in Sections 5.1.1 and 5.1.3) for severity, causal relationship to the study drug, and expectedness. The onset and resolution dates of the event and the action taken in response to the event will be documented. If the event has not resolved by the final study visit, it will be documented as “ongoing” on the CRF, however, follow-up of the SAE must continue until resolved. Information recorded on the CRF must be substantiated in the source documents.

**The SAE Report form completed for that event must be faxed by the principal investigator or his/her designee, within 24 hours (one calendar day) of the clinical site becoming aware of the event, to the local medical monitor and to Drug Safety Solutions. The AE CRF should be completed with all information known at the time; the Supplemental SAE Report (paper form) should be completed and both forms faxed (even if all information concerning the event is not yet known) within the first 24 hours of awareness of the event.**

**Fatal or life-threatening serious adverse events that the investigator suspects are related to the study drug should be telephoned to the medical monitor immediately upon the investigator’s awareness of the event. If the medical monitor is required by the protocol or chooses to suspend enrollment s/he shall immediately create a written memorandum for record to the study file and telephonically notify the sponsor of this act.**

**Contact information for all safety personnel are contained in the Team Contact List which will be stored on site in the Site Regulatory Binder and maintained by the study sponsor.**

Investigators must not wait to collect additional information to fully document the event before notifying the local medical monitor and Drug Safety Solutions of a serious adverse event. The initial notification should include the following (at minimum):

- Protocol number and name and contact number of the investigator
- Subject ID number (and initials and date of birth, if available)
- Date subject received study drug
- Serious adverse event(s) and date of event onset
- Current status of subject

The sponsor has authorized Drug Safety Solutions to execute its responsibilities for safety report submission to the appropriate regulatory authorities within specific time periods of being notified of the event (within 7 or 15 calendar days depending the character of the SUSAR); therefore, it is important that the investigator submit additional information requested as soon as it becomes available.

The sponsor will notify the SMC of all SUSARs within 3 working days of becoming aware of an event and will provide all follow-up information in a timely manner.

### **5.12 Other Events Requiring Immediate Reporting**

The investigator must report the following events by faxing the appropriate form to the medical monitor within 24 hours of becoming aware of the event:

- Withdrawal of consent during the study (Immediately Reportable Event Form)
- Emergency unblinding (Immediately Reportable Event Form)
- Protocol violation affecting the safety of a subject or involving the vaccination process (Immediately Reportable Event Form)
- Adverse event thought to be an allergic reaction to the study drug (Immediately Reportable Event Form, unless event meets SAE criteria)
- Any event that, in the opinion of the investigator, precludes further administration of the study drug (Immediately Reportable Event Form, unless meets SAE criteria)
- Pregnancy (Immediately Reportable Event Form, and Pregnancy Notification Form)

### **5.13 Adverse Event Treatment, Follow-up, and Outcome**

Treatment of any adverse events will be determined by the investigator using his/her best medical judgment and according to current clinical practice guidelines. All treatments as well as follow-up will be recorded in the appropriate CRF.

Adverse events will be considered resolved when the condition returns to normal or returns to the subject's baseline status as established on Study Day 0, or when the condition has stabilized with the expectation that it will remain chronic.

The investigator will continue follow-up on adverse events, including laboratory abnormalities and solicited adverse events, until the event has resolved, is otherwise satisfactorily explained, or the subject completes the study.

Follow-up for serious adverse events must continue until resolution and the outcome reported to the sponsor, even if this extends beyond the serious adverse event reporting period (i.e., after the final study visit). For analysis purposes, the outcome for serious adverse events will be determined on the final study visit.

Outcome of all adverse events will be classified as one of the following:

- Resolved
- Resolved with sequelae
- Ongoing
- Death

If at any time after completion of the serious adverse event reporting period (the final study visit) the investigator becomes aware of a serious adverse event that is suspected by the investigator to be related to the study drug, the event must be reported to the sponsor.

#### **5.14 Follow-up of Subjects Who Become Pregnant**

If a subject becomes pregnant during the study, she should be encouraged to continue in the study for safety follow-up. Follow-up should continue for pregnancy outcome including premature terminations, and data are to be included in the safety reports.

The investigator must notify the local medical monitor of the pregnancy immediately (even if already known to have resulted in spontaneous or elective abortion) by faxing the Pregnancy Notification Form to the medical monitor. At a minimum, the estimated date of conception, the estimated due date, and the date the subject received the study drug should be provided.

If a subject becomes pregnant, she will not have any interventions done as normally mandated by the protocol. The subject will undergo all other evaluations according to the Summary Schedule(s) of Evaluations.

The health status of the mother and child, the date of delivery, and the child's sex, birth weight and multiparity should be reported to the safety monitor after delivery, using a Pregnancy Notification Form. If delivery occurs before the final study visit, the subject should continue to be followed for SAEs through the final study visit unless withdrawal of consent has occurred. If delivery occurs after the final study visit, the investigator should attempt to maintain contact with the subject to obtain information after delivery.

Pregnancy will not be recorded as an adverse event. However, pregnancy outcomes will be recorded in the World Wide Safety Database. If the pregnancy results in a miscarriage or a planned termination, the event (spontaneous abortion or elective abortion) will be reported as an adverse event or serious adverse event per the investigator's judgment (e.g., if it was a medically important or life-threatening event that meets the definition of a serious adverse event).

A congenital anomaly or birth defect (i.e., an adverse finding in a child or fetus of a subject exposed to the study drug before conception or during pregnancy) must be reported as a serious adverse event.

If it is determined after completion of the study that a subject became pregnant during the study, the subject should notify the investigator. The pregnancy must be reported to the local medical monitor and the status of the mother and child after delivery will be obtained and reported, when possible.

### **5.15 Subject Daily Temperature Monitoring**

Subjects will receive a digital thermometer to be used during the specified post-vaccination. Temperature should be taken and the time recorded as soon as possible after awakening and before the ingestion of hot or cold liquids during the solicited adverse event period after Study Drug administration.

## **6 PAUSING AND STOPPING RULES**

These rules govern the pausing and stopping of study drug administration at any time during the study such as between doses (for multiple dose studies) for an individual, between individuals within a single dose group, and between dose groups.

### **6.1 Safety Pausing Rules**

The principal investigator and/or local medical monitor will pause administration of study drug in the trial if:

1. It is determined that a SUSAR occurred  
*OR*
2. It is determined that a serious adverse event *OR* a Toxicity Grade 3 or 4 event (except for elevated CPK and visually interpreted urine dipstick findings) *OR* an adverse event pattern of concern occurred *AND* is judged to be *POSSIBLY*, *PROBABLY* or *DEFINITELY* related to study drug

If the principal investigator and/or local medical monitor pauses administration of study drug in the study, he or she will record this in a memorandum to the study file and notify the sponsor who will then convene the SMC. The FDA must be notified if the Study is paused for safety reasons. The FDA must be notified if the Study is then resumed. If additional clinical information becomes available that reduces the principal investigator's assessment of causality, severity or toxicity grade such that study pausing is no longer required, then the principal investigator, with the agreement of the local medical monitor, may resume study drug administration, record this in a memorandum to the study file, and notify the sponsor.

Since the medical monitor reviews data from all the sponsor's trials, he or she may become aware of an adverse event pattern of concern not appreciated by the principal investigator or local medical monitor. If the global medical monitor independently determines that an adverse event pattern of concern that is judged to be *POSSIBLY*, *PROBABLY* or *DEFINITELY* related to study drug has occurred, the global medical monitor will pause administration of study drug in the trial, record the study pause in a memorandum to the study file, and notify the local medical monitor, principal investigator and sponsor who will convene the SMC.

## 6.2 Safety Stopping Rules

The rules for stopping further enrollment and study drug administration by the SMC are below:

- Death in any subject unless the SMC determines it is UNRELATED to SYN023
- An anaphylactic reaction to SYN023 in any subject
- A severe (Toxicity Grade 3 or 4) or serious adverse event (except for CPK elevations and visually interpreted urine dipstick findings) unless the SMC determines it is UNRELATED to SYN023.
- A potentially life-threatening adverse event or serious adverse event unless the SMC determines it is UNRELATED to SYN023.
- A pattern of significant symptoms, physical findings or laboratory abnormalities (adverse events) that, although individually minor, collectively represent a safety concern in the opinion of the investigator or the medical monitor and are judged by the SMC to be DEFINITELY, PROBABLY or POSSIBLY related to SYN023

The SMC may recommend resumption of study drug administration if the study pause was for reasons less severe than those in the SMC stopping rules. The SMC may recommend resumption of enrollment if it judges that changes to the study protocol will eliminate or greatly reduce the safety risks specified in the stopping rules. In the absence of study protocol changes the SMC must follow the SMC study stopping rules.

If a decision to resume study enrollment and study drug administration is made the SMC will record their judgment in a memorandum to the study file and notify the sponsor. The SMC memorandum will be forwarded to the medical monitor and principal investigator. The clinical site will be allowed to resume activities upon receipt of written notification from the sponsor. The U.S. FDA will be informed in writing when:

1. The study is stopped
2. The decision is made by the SMC to resume or discontinue study activities

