## **3.3 Study Randomization and Sentinel Subjects**

Subjects will be randomized to the study based on a randomly-generated sequence of subject identification numbers (randomization schedule). The randomization schedule will be prepared by a statistician who will not be involved in the analysis of the study in order to maintain the blind of the study team. A subject is considered randomized when a subject identification number has been assigned to them on Study Day 0. The first four subjects entered into the study (sentinel subjects) will be randomized such that a subject each receives one of the four possible regimens. Safety information on these sentinel subjects through study day 14 will be collected and reviewed by the medical monitor and principal investigator before the remainder of the trial is enrolled.

Subjects who withdraw from the study or are discontinued may be replaced by modification of the remaining randomization schedule. Unless there is reason to pause the study, based on the study pausing rules as outlined in Section 6.1, then the principal investigators may proceed to enroll all of the subjects.

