#### **5.1.4 Safety Monitoring Committee**

If study drug administration is paused (see safety pausing rules in Section 6.1) by the principal investigator, the local medical monitor, or the global medical monitor, an SMC will be convened. The SMC composition is described in an SMC charter. The voting members cannot be directly involved with the conduct of the study. Voting members cannot be employees of the sponsor. Additional subject area experts may be present to provide expertise if requested by the SMC. The SMC may review an individual SAE or it may choose to review adverse events, serious

adverse events, solicited adverse events, and laboratory and vital signs data. The SMC may unblind any amount of safety information needed to conduct their assessment. Only the SMC and the independent statistician responsible for preparing these analyses would be unblinded during these reviews. All procedures associated with this review, including objectives, data handling, and elements to be included for review will be documented in SMC minutes.

Based on its review and the protocol stopping rules (Section 6) the SMC will make recommendations in the SMC minutes to the sponsor regarding further conduct of the study and further administration of study drug. The conclusions of the SMC will be communicated to the investigators and the Institutional Review Boards/Ethics Committees and the national regulatory authority. The sponsor agrees to abide by the decision of its SMC and any directives issued by the national regulatory authority, the Institutional Review Board or Ethics Committee.

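### Protocol 6.1 and 3.3 let dosing resume, or enrollment proceed, before the SMC has made the causality finding that 6.2 reserves to it

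*Protocol*

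**What the plan says.** **Protocol 6.2** lists the rules under which the SMC stops enrollment and study drug. The first is "Death in any subject unless the SMC determines it is UNRELATED to SYN023". The third rule (Grade 3 or 4 or serious events, apart from CPK rises and visually read dipstick findings) and the fourth (potentially life-threatening events and SAEs) carry the same exception. In each, the finding of unrelatedness belongs to the SMC. Unless the protocol is changed, the SMC is bound by these rules. On restart after an SMC decision, the section says: "The clinical site will be allowed to resume activities upon receipt of written notification from the sponsor".

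**Protocol 6.1** governs pauses by the investigator and the monitors. Whoever pauses must file a memorandum and "notify the sponsor who will then convene the SMC". If new clinical information lowers the investigator's rating of causality, severity or grade so that no pause is needed, the investigator, "with the agreement of the local medical monitor, may resume study drug administration, record this in a memorandum to the study file", and then tells the sponsor.

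**Protocol 5.1.4** ties the convening of the SMC to a pause: "If study drug administration is paused (see safety pausing rules in Section 6.1) by the principal investigator", or by the local or global monitor. Otherwise review is optional: "The SMC may review an individual SAE or it may choose to review adverse events".

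**Protocol 3.3** says that sentinel safety data through Day 14 "will be collected and reviewed by the medical monitor and principal investigator before the remainder of the trial is enrolled". Unless there is reason to pause, "based on the study pausing rules as outlined in Section 6.1, then the principal investigators may proceed to enroll all of the subjects". Section 6.2 is not named.

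**Protocol 5.2** obliges the medical monitor to keep the SMC aware of new safety data. **Protocol 5.11** gives the SMC notice within 3 working days, for SUSARs.

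**The concern.** Section 6.2 gives the causality decision on the gravest events to a body whose voting members may be neither sponsor employees nor directly involved in conducting the study (5.1.4). Sections 6.1 and 3.3 hand the practical decisions, whether to restart and whether to release the remaining subjects, to the investigator and the medical monitor. The monitor is the sponsor's representative (5.1.3). A site that follows 6.1 and 3.3 to the letter can therefore dose further subjects before the SMC has made the finding that 6.2 calls for.

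There is a realistic path to this. Vaccine is given within 75 minutes after study drug (3.5), and study drug means SYN023 or RIG. Section 5.5 itself foresees SAEs attributed to the vaccine. An SAE that both assessors put down to the vaccine opens no pause under 6.1, yet it is on the 6.2 list. Attribution is hardest when products are given that close together, and that is where an independent ruling is worth most.

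**Working it through.** The plan gives no figure to reproduce. The check is a trace of the routes to the SMC, a comparison of the restart rules, and a count of who could be affected.

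**1. Routes to the SMC when both local assessors rate the event not related or unlikely related (5.5 counts both as unrelated)**

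- 6.1, first trigger, a SUSAR: closed, because 5.10 requires relatedness.
- 6.1, second trigger, an SAE, Grade 3 or 4 event or pattern of concern: closed, because it must be judged at least possibly related to study drug.
- 6.1, global monitor's pause: closed, because it needs a pattern judged related.
- 5.11, notice to the SMC within 3 working days: closed, because it covers SUSARs.
- 5.11, 24-hour SAE report: it goes to the local medical monitor and the safety contractor; the SMC is not a named recipient.
- Investigator's pause on suspicion (5.1.1), monitor's choice to suspend enrollment (5.11), SMC's own choice to review an SAE (5.1.4): open, but discretionary.
- 5.2, awareness duty: open and mandatory whatever the causality rating, with no limit in hours or days.

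One mandatory route remains in the readable text. If either assessor rates the event possible or higher, the higher rating governs (5.5), the 6.1 pause is mandatory and the SMC is convened.

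**2. Restart rules side by side**

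- Under 6.1, a downgrade by the investigator plus the local monitor's agreement allows dosing to resume; the sponsor is told, and the FDA must be notified of both the pause and the resumption. No SMC decision is required first.
- Under 6.2, the SMC decides, records its judgment and informs the sponsor, and the site waits for the sponsor's written notice.

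A related SAE shows the overlap. It triggers a 6.1 pause and is also on the 6.2 list. If the rating is lowered before the SMC meets, 6.1 permits restart while the 6.2 determination is outstanding. No sentence says which rule governs.

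**3. The sentinel gate**

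Section 3.3 makes release turn on 6.1. By step 1, a sentinel SAE that both assessors call unrelated gives no reason to pause under 6.1, so enrollment may proceed with the 6.2 question open.

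**4. Exposure**

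Study drug is a single Day 0 dose, so only subjects not yet dosed can be protected. Inputs from Protocol 2.2 and 3.3: 160 planned, 40 per arm, 4 sentinels, one per regimen.

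- Undosed at the gate: 160 − 4 = 156, and 156 / 160 = 97.5%.
- Of these, due SYN023: 2 × (40 − 1) = 78.

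Both counts are before replacements and fall to 0 when the last subject is dosed. The documents give no enrollment rate and no expected SAE rate, so no probability can be attached.

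**The case against.** The strongest reply is that this is a deliberate two-tier scheme. Section 6.1 binds the investigator and monitors, 6.2 binds the SMC, and different thresholds at different tiers are a design choice. Section 5.2 delivers the event to the SMC, and 6.2 then obliges the SMC to stop unless it finds the event unrelated. Around this stand the 24-hour report to an unblinded monitor, the discretionary pauses, and the powers of the IRB and the regulator to suspend. A 6.1 restart also needs new clinical information and the monitor's agreement. Finally, Appendix B (the SAE reporting scheme) and the SMC charter could not be read for this review, and either is a natural place for a referral trigger.

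Much of this stands. Three stronger readings that a reader might infer are not supported:

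- *That the SMC could be left uninformed, or free to ignore the event.* Section 5.2 is mandatory, and once aware the SMC must apply 6.2. What the readable text lacks is a deadline for that step and any hold on dosing meanwhile.
- *That 6.1 and 6.2 flatly contradict each other on when dosing must stop.* They address different actors. The defect is that precedence is unstated where they overlap on restart and sentinel release.
- *That no timed trigger exists anywhere.* The unread charter and appendix prevent that conclusion.

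The two-tier argument does not answer the restart and sentinel rules. Both are operative text, and each lets the lower tier act before the upper tier has made a finding reserved to it.

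**Conclusion.** The point holds in limited form. The downgrade route in 6.1 and the release rule in 3.3 can each bypass, at least for a time, the determination that 6.2 gives to the SMC. When both local assessors call the event unrelated, the only mandatory link visible is the undated duty in 5.2.

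The case is narrow: it needs a grave event that both assessors rate below possible, or a downgrade that both accept before the SMC rules. The counts of 156 subjects, 78 of them due SYN023, bound the exposure at the sentinel gate; they do not estimate harm. Half of the 156 are due licensed RIG, whereas the 6.2 test concerns SYN023. The conclusion assumes that the charter and Appendix B add no timed referral. If they do, the undated link is closed, but the 6.1 and 3.3 wording still needs attention unless those documents also govern restart and release. I would recommend the change because it bears on subject safety and needs only wording.

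**What to change.** 1. **Protocol 6.1:** state that dosing paused for a death, an SAE or a potentially life-threatening event may not resume on a local downgrade until the SMC has recorded its 6.2 determination.
2. **Protocol 3.3:** make release of the remaining subjects depend on there being neither a 6.1 pause nor a pending 6.2 determination.
3. **Protocol 5.1.4 or 5.11:** extend the existing 3-working-day SMC notice from SUSARs to all deaths, SAEs and potentially life-threatening events, whatever the local rating, and require the SMC to record a causality determination. If the charter or Appendix B already does this, cite it instead.

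Item 3 is needed because item 1 cannot reach an event that was never paused under 6.1. Even with all three, an event that both assessors call unrelated would not by itself hold dosing after the sentinel stage; the change puts a limit on how long the SMC can go without notice. Non-serious Grade 3 or 4 events share the gap under the third 6.2 rule. They are left out here to limit the SMC's workload.

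The cost is a few extra SMC reviews and possibly short dosing delays. No subjects, visits or tests are added.
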